4.2. Primary Endpoint Analysis

The primary efficacy endpoint analysis will be based on the FAS.

The analyses for participants in the LN cohort and participants in the IgAN cohort will be conducted and reported separately. Participants in each disease-specific cohort will be analyzed as randomized, regardless of actual treatment received.

The primary analysis of the primary efficacy endpoint will be performed for each disease-specific cohort at the end of the 26-week Blinded Initial Evaluation Period after all participants in the disease-specific cohorts have completed or withdrawn from the 26-week Blinded Initial Evaluation Period. The estimand for the primary analysis is defined in Table 3.

Table 3: Estimand for Primary Analysis

Estimand	Treatment	Population	Variable	Intercurrent Event	Population-level Summary
Primary analysis	ALXN2050 180 mg, Placebo	FAS	Percentage change in proteinuria from baseline to Week 26	 Receipt of additional standard-of-care therapy (LN cohort only) Treatment discontinuation 	Difference in mean of percentage change in proteinuria between ALXN2050 180 mg bid treatment and placebo groups

Abbreviations: bid = twice daily; FAS = Full Analysis Set; LN = lupus nephritis

4.2.1. Derivation of Endpoint(s)

The primary endpoint for the study is percentage change from baseline to Week 26 in proteinuria based on 24-hour urine collection(s) at each time point.

Proteinuria will be measured by absolute urine protein (UP) in g/day as well as by urine protein-to-creatinine ratio (UPCR) in g/g for each disease cohort as follows:

- For the LN cohort, proteinuria measured by UPCR as well as by UP is derived from a single 24-hour urine collection at Screening and the mean of 2 separate 24-hour urine collections within 3 weeks prior to or 1 week after Week 26 Visit to assess the primary endpoint. Two separate 24-hour collections should be obtained at Week 50 Visit to assess the secondary endpoint, as long as they are collected within 3 weeks prior to Week 50 Visit. Additional 24-hour urine collections are also scheduled for Weeks 102 and 154.
- For the IgAN cohort, proteinuria measured by UP as well as UPCR is derived from the mean of 2 valid 24-hour urine collections during the Screening Period and within 3 weeks prior to Week 26 Visit to assess the primary endpoint. Two separate 24-hour collections should be obtained at Week 50 Visit to assess the secondary endpoint, as long as they are collected within 3 weeks prior to or 1 week after Week 50 Visit. Additional 24-hour urine collections are also scheduled for Weeks 102 and 154.

For the primary endpoint, proteinuria will be based on UPCR for the LN cohort and UP for the IgAN cohort. For both cohorts, the natural logarithm will be used to transform proteinuria values before the analysis to reduce skewness. When 2 valid 24-hour urine collections are required and only 1 valid collection is available at the visit, then this value will be used for analysis.

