Pregnancy test (WOCBP only)	Х	Х	Х	х	X	X	X	Х	X		Serum tests required at Screening and ED; urine tests at all other visits. (Section 8.2.6)

Table 1: Schedule of Activities During Screening and the Blinded Initial Evaluation Period: Screening to Week 26 Visit (LN Cohort)

Period	Screen- ing		Initial Evaluation Period								Notes
Visit	1	2	3	4	5	6	7	8	9	Evaluation for Renal	Unscheduled visits can be performed as needed. An ED Visit is required if participant discontinues study early.
Week	Up to 6 W		W2	W4	W8	W12	W16	W20	W26/ ED ^b	for Kenal Flare and Extrarenal	
Days and Window	D -42 to -1	D1	D15 ± 3	D29 ± 3	D57 ± 5	D85 ± 5	D113 ± 5	D141 ±5	D183 ± 5	SLE Flare Assessment Visit ²	
FSH test ^d	х										Only for females who are not WOCBP (Section 8.2.4.4).
HIV, HCV, and HBV	X										
Dispense participant safety card	X										Instruct participants to carry safety card at all times and bring it to scheduled visits (Section 8.2.7).
Efficacy Assessments											
24-hour urine collection ^e	х								X	х	One collection is needed as soon as possible during Screening. Two separate collections must be obtained within 2 weeks prior to the Week 26 Visit. (Section 8.1.1.1).
Morning spot urine sample	X	X	X	X	X	X	X	X	X	X	Two consecutive spot urine samples at Week 16 (Section 8.1.2).
eGFR (measured by serum creatinine)	х	х	х	х	х	х	х	Х	х	X	At Week 26, the first creatinine sample for eGFR will be obtained within 2 weeks prior to Week 26 study visit and the second creatinine sample will be obtained on the study visit day (Section 8.1.3).
Predose blood sample for serum clinical complement tests	Х	Х	Х		X		Х		X	X	Section 10.2.

Table 1: Schedule of Activities During Screening and the Blinded Initial Evaluation Period: Screening to Week 26 Visit (LN Cohort)

Period	Screen- ing			Initi	al Evalu		Notes					
Visit	1	2	3	4	5	6	7	8	9	Evaluation for Renal	Unscheduled visits can be performed	
Week	Up to 6 W		W2	W4	W8	W12	W16	W20	W26/ ED ^b	Flare and Extrarenal	Flare and Extrarenal	as needed. An ED Visit is required if participant discontinues study early.
Days and Window	D -42 to -1	D1	D15 ± 3	D29 ± 3	D57 ± 5	D85 ± 5	D113 ±5	D141 ± 5	D183 ± 5	SLE Flare Assessment Visit ^a		
Monitor for Renal Flare and/or Extrarenal SLE Flare ^a			Continuous monitoring							х	Refer to Section 8.1.6 and Section 8.1.7 for definitions. Document use of additional standard of care therapy and/or repeat biopsy, if applicable (Section 6.5.4).	
Safety Assessments												

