4.1.1. Screening

Participants will be screened for eligibility for up to 6 weeks during the Screening Period. For participants in the LN cohort, all screening laboratory assessments should be performed as soon as possible after signing of the informed consent form (ICF). All participants in the LN cohort should be randomized as soon as possible once eligibility is confirmed.

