6.5.3.1. Allowed Concomitant Therapy for LN Cohort

During the course of the study, participants in the LN cohort will receive allowed concomitant therapy consistent with the standard of care for induction and maintenance treatment of LN.

- For participants who have not started corticosteroid induction treatment prior to Screening:
 - Participants will receive a cumulative dose of 1 g of methylprednisolone IV administered in 1 or multiple divided doses or oral equivalent during the Screening Period (prior to Day 1).
 - During the Screening Period and no later than Day 2, all participants will receive oral corticosteroids with prednisone or prednisone equivalent with starting doses as outlined in Table 12. The starting minimum and maximum doses allowed are

- 30 mg/day and 60 mg/day, respectively. A corticosteroid taper will commence at Week 2 (Day 14). From Week 12 to Week 26, the target dose is 7.5 mg/day. Following Week 26, participants may remain on 7.5 mg/day or continue to taper at the clinical discretion of the Investigator until Week 46. From Week 46 to Week 50, the dose of corticosteroids must not be changed.
- During the Screening Period and no later than Day 1, participants will receive a cumulative dose of 1 to 1.5 g/day of MMF any time after completion of the IV methylprednisolone during the Screening Period and no later than Day 1. The dose can be administered in multiple divided doses. Participants will continue to receive 1 to 1.5 g/day for 1 week.
- After receiving 1 to 1.5 g/day for 1 week, the dose will be titrated per the discretion of the Investigator to a cumulative dose up to 3 g/day of MMF no later than by Week 4 (Day 28). The dose can be administered in multiple divided doses. Participants will continue to receive 1.5 to 3 g/day of MMF until Week 50, after which it may be decreased or discontinued based on the Investigators' judgment and the KDIGO clinical practice guidelines (KDIGO, 2012).
- For participants who have initiated corticosteroid induction treatment prior to Screening and do not meet Exclusion Criterion 28 (Section 5.2):

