8.1.2. Spot Urine Sample (Both Cohorts)

Urinary protein, albumin, and creatinine levels from morning spot urine samples prior to dosing will be measured at the time points specified in the SoA (Section 1.3) to assess the effect of study intervention on UPCR and UACR.

Two consecutive spot urine samples will be obtained for participants in both disease cohorts at Week 16 for the LN cohort and at Week 18 for the IgAN cohort.

The UPCR and UACR results will be recorded in the participant's eCRF.

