4.2.2. Main Analytical Approach

An analysis of covariance (ANCOVA) will be used for the primary efficacy analysis to compare reductions in proteinuria between the ALXN2050 180 mg bid treatment and placebo groups. The ANCOVA model will include change from baseline in log-transformed proteinuria as the response variable and will adjust for baseline log proteinuria and the randomization stratification factor. The treatment effect will be evaluated using the least-squares mean difference between treatment groups. The point estimate and 2-sided 90% CI for the mean difference of log-transformed proteinuria will be back transformed (via exponentiation) to obtain the geometric mean ratio (GMR) and corresponding 2-sided 90% CI. The values will then be expressed as percentage change in adjusted geometric mean of proteinuria at Week 26 relative to baseline.

The analysis will be performed for both proteinuria measures, UPCR and UP, in both cohorts even though the primary endpoint will be measured by UPCR for the LN cohort and by UP for the IgAN cohort.

The randomization stratification factor will be based on strata verified by laboratory and allowed concomitant therapy data from electronic case report form (eCRF). Sensitivity analysis may be performed using strata as randomized in the interactive response technology.

The data after the intercurrent events will be treated as missing, and all the missing data will be imputed according to the following assumptions:

In the LN cohort, only data up to the point of additional standard of care therapy will be included as observed for participants who receive additional standard of care therapy due to renal flare. Data on or after additional standard of care therapy for these participants is treated as missing regardless of whether the data is collected or not. The measurement performed at the time of renal flare (ie, proteinuria value from the 24-hour urine collection) will be carried forward to all subsequent visits.

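### The LN primary ANCOVA and its imputation models leave out the Day 1 pre-dose spot UPCR, although induction can start or change between the screening baseline and first dose; the cost is precision, not bias

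*SAP*

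**What the plan says.** - **Baseline.** SAP 4.2.1: "proteinuria measured by UPCR as well as by UP is derived from a single 24-hour urine collection at Screening". The Week 26 value is the mean of two 24-hour collections. The LN schedule in protocol Table 1 has no 24-hour collection on Day 1, and its note on the screening sample reads "One collection is needed as soon as possible during Screening".
- **Length of Screening.** Protocol 4.1.1: "Participants will be screened for eligibility for up to 6 weeks during the Screening Period". The same section adds: "All participants in the LN cohort should be randomized as soon as possible once eligibility is confirmed".
- **Treatment before first dose.** For LN participants not yet on corticosteroid induction, protocol 6.5.3.1 says: "Participants will receive a cumulative dose of 1 g of methylprednisolone IV". This falls before Day 1. MMF starts by Day 1 and oral prednisone by Day 2. A second group is described as "For participants who have initiated corticosteroid induction treatment prior to Screening and do not meet Exclusion Criterion 28". Its members have already begun induction when the baseline urine is taken, and some have MMF raised during Screening.
- **Primary model.** SAP 4.2.2: the ANCOVA "will adjust for baseline log proteinuria and the randomization stratification factor". For LN, that factor is whether corticosteroid induction began before or during Screening. The imputation models in SAP 6.4.3 to 6.4.5 use baseline, stratum and Week 26, plus treatment in 6.4.3 and 6.4.5.
- **Spot UPCR.** Protocol 8.1.2: "creatinine levels from morning spot urine samples prior to dosing will be measured". Table 1 schedules this at Screening, Day 1 and each later LN visit. SAP 4.3.1.1 analyses spot UPCR by MMRM to Week 50, and SAP 6.2.2.2 summarises baseline spot UPCR. Neither the primary ANCOVA nor any sensitivity analysis in SAP Table 4 uses the Day 1 value.

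**The concern.** Change from the screening 24-hour UPCR to Week 26 can contain two parts: what happened under induction before first dose, and what happened on study treatment. The first part differs between people, because the interval, the treatment received in it and the response to it all differ. A two-level stratum removes the average difference between its levels but not the spread within a level. The screening value predicts some of that spread but cannot reflect a response that has not yet occurred.

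The Day 1 sample is the only scheduled measure of proteinuria taken after this interval and before dosing, so study treatment cannot have affected it. Leaving it out gives up whatever residual variance it would explain, in a comparison sized at about 80% power.

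It also bears on missing data. SAP 4.2.2 rests its missing-at-random imputation on the relevant observed factors being in the model, and pre-dose proteinuria after the run-in is a plausible one. SAP 4.1.4 assumes missing at random for outcomes lost to the dosing pause as well.

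**Working it through.** **Inputs from the plan (protocol 9.2, SAP section 5).** LN ratios to baseline are 0.60 (placebo) and 0.40 (180 mg). SD of log change is 0.60, taken from an IgAN source because no log-scale LN figure was available. There are 30 randomised per arm with 10% dropout, and a 1-sided 0.05 two-sample t-test.

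**Step 1. Reproduce the stated power.**
- Effect: ln(0.60/0.40) = 0.405.
- Evaluable per arm: 30 × 0.9 = 27.
- Noncentrality: 0.405 / (0.60 × √(2/27)) = 2.483, with 52 degrees of freedom.
- Power: 79.0% by noncentral t, 79.9% by the normal approximation. The stated figure of about 80% reproduces.

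**Step 2. Add the covariate.** Let r be the partial correlation of log Day 1 spot UPCR with the Week 26 outcome, given the covariates already in the model. The residual SD becomes 0.60 × √(1 − r²). The documents give no r, so every row below r = 0 is an assumption. The 90% CI half-width is 1.675 × SD × √(2/27).

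| r (assumed) | Residual SD | Power | 90% CI half-width, log scale |
|---|---|---|---|
| 0 | 0.600 | 79.0% | 0.273 |
| 0.1 | 0.597 | 79.3% | 0.272 |
| 0.2 | 0.588 | 80.4% | 0.268 |
| 0.3 | 0.572 | 82.2% | 0.261 |
| 0.5 | 0.520 | 88.2% | 0.237 |

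**Step 3. Only some participants gain.** If half the cohort starts induction during Screening and only they benefit, the average residual SD is 0.60 × √(1 − 0.5r²). At r = 0.3 this is 0.586 (power 80.6%), and at r = 0.5 it is 0.561 (83.5%). The half share is assumed, as the documents do not give the split.

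**Step 4. A different starting point.** The 0.60 is the SD in an unadjusted t-test, whereas r is defined after adjustment. If the planned covariates already correlate 0.4 with the outcome (assumed), the residual SD is 0.550 and power is 84.8% before any change. A further r of 0.2 gives SD 0.539 and 86.1%, a gain of 1.3 points.

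**Step 5. Cost when the covariate is useless.** One degree of freedom: the critical t moves from 1.6747 (52 df) to 1.6753 (51 df).

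**The case against.** The case for leaving the plan alone is substantial. The run-in comes before study treatment, so randomisation balances it on average. The plan already adjusts for screening UPCR and for induction timing, which is the design variable for this very issue. Spot UPCR is not ignored: under the baseline rule in SAP 6.1.2 the spot baseline would be the Day 1 sample, so the spot MMRM compares arms from a point after the run-in, and the baseline table would show a chance imbalance. The gain rests on an assumed correlation applied to an unadjusted SD from another disease, and 27 evaluable per arm is not assured after the dosing pause of 06 September 2024.

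All of this stands, and it limits the size of the point. It does not remove it. A secondary spot-urine analysis does not sharpen the primary 24-hour comparison, and a baseline table shows an imbalance without adjusting for it.

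Stronger readings are tempting, but the documents do not support them:
- *That the baseline is usually taken before induction.* The order of urine collection and methylprednisolone is not fixed, the split between strata is not given, and one stratum began induction before Screening.
- *That six weeks of response is involved.* Six weeks is the maximum, and LN participants are to be randomised promptly. MMF may start as late as Day 1 and oral prednisone as late as Day 2, so exposure before first dose could be days.
- *That the pre-dose response is wholly unexplained.* The existing covariates absorb part of it.
- *That the treatment contrast is biased.* It is not. Only the within-arm percentage change mixes run-in response with on-study change.

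**Conclusion.** The point holds as a matter of precision. An informative pre-dose value, already scheduled for every LN participant, is missing from the LN primary ANCOVA and from the imputation models that support it. The plan is valid without it.

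The documents do not allow the loss to be sized. Taking 0.60 as the SD without the covariate, and 27 evaluable per arm, the gain in power is about 1 point at r = 0.2 (79.0% to 80.4%), 3 points at 0.3 (82.2%) and 9 points at 0.5 (88.2%). It is smaller if only one stratum gains or if the existing covariates already do much of the work, and close to nothing if r is near zero. Because the possible gain is moderate and the cost negligible, the change is worth making before unblinding.

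**What to change.** 1. Keep the LN endpoint as change from the screening 24-hour UPCR. A spot value should not replace the 24-hour baseline, because the two are different measures.
2. In SAP 4.2.2 and 6.4.1, add log Day 1 pre-dose spot UPCR as a second continuous covariate in the LN primary ANCOVA.
3. Carry it into the multiple-imputation, placebo-based and tipping-point models (SAP 6.4.3, 6.4.4 and 6.4.5), so that the primary and sensitivity analyses condition on the same information.
4. If the Day 1 value is missing, use the last pre-dose spot UPCR under the SAP 6.1.2 rule, and report how often this happens. Such a value may predate the run-in, so the count matters.
5. Summarise by arm the change in spot UPCR from Screening to Day 1, so that the within-arm percentage changes can be read with the run-in response in view.

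Cost: a SAP amendment before unblinding, covering one model and three imputation specifications, one extra summary table and one degree of freedom. The samples are already scheduled, so no protocol amendment or new data collection is needed.

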4.2.2. Main Analytical Approach

An analysis of covariance (ANCOVA) will be used for the primary efficacy analysis to compare reductions in proteinuria between the ALXN2050 180 mg bid treatment and placebo groups. The ANCOVA model will include change from baseline in log-transformed proteinuria as the response variable and will adjust for baseline log proteinuria and the randomization stratification factor. The treatment effect will be evaluated using the least-squares mean difference between treatment groups. The point estimate and 2-sided 90% CI for the mean difference of log-transformed proteinuria will be back transformed (via exponentiation) to obtain the geometric mean ratio (GMR) and corresponding 2-sided 90% CI. The values will then be expressed as percentage change in adjusted geometric mean of proteinuria at Week 26 relative to baseline.

The analysis will be performed for both proteinuria measures, UPCR and UP, in both cohorts even though the primary endpoint will be measured by UPCR for the LN cohort and by UP for the IgAN cohort.

The randomization stratification factor will be based on strata verified by laboratory and allowed concomitant therapy data from electronic case report form (eCRF). Sensitivity analysis may be performed using strata as randomized in the interactive response technology.

The data after the intercurrent events will be treated as missing, and all the missing data will be imputed according to the following assumptions:

In the LN cohort, only data up to the point of additional standard of care therapy will be included as observed for participants who receive additional standard of care therapy due to renal flare. Data on or after additional standard of care therapy for these participants is treated as missing regardless of whether the data is collected or not. The measurement performed at the time of renal flare (ie, proteinuria value from the 24-hour urine collection) will be carried forward to all subsequent visits.

• In both the LN and IgAN cohorts, data occurring on or after treatment discontinuation will be treated as missing. It is assumed that study participants follow the behavior of their randomized arm. All the missing data will be imputed through multiple imputation (MI) under MAR assumption. Participants with missing data can be modeled based on similar participants with available data if relevant observed factors are accounted for in the model. This MI procedure can be performed in 3 steps: 1) Impute missing data (eg, use PROC MI, *m* times); 2) Analyze each of the *m* complete data sets (eg, use PROC ANCOVA); and 3) Combine results across *K* multiply imputed datasets using Rubin's rule (eg, PROC MIANALYZE).

4.2.3. Sensitivity Analyses

Table 4 summarizes the sensitivity analyses that will be produced for the primary endpoint.

All sensitivity analyses will be based on an ANCOVA model using the FAS population; in addition sensitivity analysis due to dosing pause will be repeated on PPS population.

Population of no impact by dosing pause will be defined as the participants who have at least one valid 24-hour urine collection obtained within 3 weeks prior to the Week 26 Visit before dosing pause.

Table 4: Sensitivity Analyses

Sensitivity Analysis	Applied Cohorts	Handling of Intercurrent Events/ Description	
Placebo-based multiple imputation + carry-forward	LN cohort only	Treatment discontinuation: Data collected on or after treatment discontinuation will be imputed using placebo-based multiple imputation. Receipt of additional standard of care therapy (LN cohort only): Data collected on or after receipt of additional standard of care therapy will be imputed using the value collected at the time of flare (carry forward).	
Placebo-based multiple imputation	LN and IgAN cohorts	Treatment discontinuation: • Data collected on or after treatment discontinuation will be imputed using placebo-based multiple imputation. Receipt of additional standard of care therapy (LN cohort only): • Data collected on or after receipt of additional standard of care therapy will be imputed using placebo-based multiple imputation.	
Tipping point analysis	LN and IgAN cohorts	Participants who receive additional standard of care therapy (LN cohort only), discontinue treatment, withdraw early, or die are assumed to have outcomes that are worse than otherwise similar participants who remain in the study or did not receive additional standard of care therapy or discontinue treatment.	

Table 4: Sensitivity Analyses

Sensitivity Analysis	Applied Cohorts	Handling of Intercurrent Events/ Description	
Per-randomized stratification analysis	LN and IgAN cohorts	Treatment discontinuation: Data collected on or after treatment discontinuation will be imputed using multiple imputation. Receipt of additional standard of care therapy (LN cohort only): Data collected on or after receipt of additional standard of care therapy will be imputed using the value collected at the time of flare (carry-forward).	
Sensitivity analysis due to dosing pause- excluding data points impacted by dosing pause	LN and IgAN cohorts	Dosing pause will be regarded as an intercurrent event, in which the analysis is similar to that of treatment discontinuation.	
Sensitivity analysis due to dosing pause- excluding participants impacted by dosing pause	LN and IgAN cohorts	The participants in the population of no impact by dosing pause will be included.	

Abbreviations: IgAN = immunoglobulin A nephropathy; LN = lupus nephritis

Further details of these sensitivity analyses are below.

- Placebo-based multiple imputation + carry-forward: The primary endpoint will be analyzed in the same manner as the primary analysis, except that data collected on or after treatment discontinuation will be assumed missing and imputed using placebobased multiple imputation where it will be assumed that outcomes occurring after treatment discontinuation will follow the trajectory of outcomes similar to the one in the placebo treatment group, taking into account observed values prior to treatment discontinuation (Ratitch, 2014).
- Placebo-based multiple imputation: The primary endpoint will be analyzed in the same manner as the primary analysis, except data collected on or after treatment discontinuation or receipt of additional standard of care therapy (LN cohort only) will be assumed missing and imputed using placebo-based multiple imputation.
- Tipping point analysis: An additional sensitivity analysis will be performed based on the delta-adjusted stress testing method (tipping point analysis). This approach assumes that participants who discontinue from ALXN2050 treatment or who receive additional standard-of-care therapy (for the LN cohort only) experience worsening, defined by a prespecified adjustment (delta) in the primary efficacy endpoint compared with the observed efficacy score of participants who continue the study to the next visit. For each value of delta, the treatment effect will be determined, and the value of delta for which the nominal 2-sided p-value crosses 0.10 will be considered

as the "tipping point" in the sense that the conclusion drawn from the primary analysis is reversed when participants who drop out or who receive additional standard-of-care therapy are assumed to experience this fixed adjustment after the discontinuation visit or receipt of additional standard-of-care therapy. After such a tipping point is determined, clinical judgment will be applied as to the plausibility of the assumptions underlying this tipping point. This methodology is expected to inform what it would take to overturn study conclusions based on varying assumptions about missing data (Ratitch, 2013; Ratitch, 2014).

- Per-randomized stratification analysis: The primary endpoint will be analyzed in the same manner as the primary analysis, except using per-randomized stratification factor from IXRS instead of verified stratification factor.
- Additional sensitivity analysis due to dosing pause:
 - The primary endpoint will be analyzed in the same manner as the primary analysis, except that the dosing pause will be regarded as an intercurrent event, in which the analysis is similar to that of treatment discontinuation.
 - Subgroup analysis: Only include participants in the population of no impact by dosing pause.

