4.3.2. Sensitivity Analysis for Key Secondary Endpoints Due to Dosing Pause

4.3.2.1. Percentage Change in Proteinuria from Baseline to Week 50 (Both Cohorts)

Two sensitivity analyses will be used to assess the impact of dosing pause.

The endpoint will be analyzed in the same manner as described in Section 4.3.1.1, except that dosing pause would be regarded as intercurrent event, in which the analysis is similar to that of treatment discontinuation.

The endpoint will also be analyzed in the same manner as described in Section 4.3.1.1, except that only the participants in the population of no impact by dosing pause are included.

4.3.2.2. Reduction in Proteinuria at Weeks 26 and 50 Compared to Baseline (Both Cohorts)

The endpoint will also be analyzed in the same manner as described in Section 4.3.1.2, except that only participants in the population of no impact by dosing pause are included.

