4.3.2.3. Change from Baseline in eGFR at Weeks 26 and 50 (Both Cohorts)

Two sensitivity analysis will be used to assess the impact of dosing pause.

The endpoint will be analyzed in the same manner as described in Section 4.3.1.3, except that dosing pause would be regarded as intercurrent event, in which the analysis is similar to that of treatment discontinuation.

The endpoint will also be analyzed in the same manner as described in Section 4.3.1.3, except that only the participants in the population of no impact by dosing pause are included.

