4.3.2.4. Complete Renal Response (LN Cohort Only)

The endpoint will also be analyzed in the same manner as described in Section 4.3.1.4, except that only the participants in the population of no impact by dosing pause are included.

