4.3.2.5. Partial Renal Response (LN Cohort Only)

The endpoint will also be analyzed in the same manner as described in Section 4.3.1.5, except that only the participants in the population of no impact by dosing pause are included.

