4.3.2.6. Partial Remission (IgAN Cohort Only)

The endpoint will also be analyzed in the same manner as described in Section 4.3.1.13, except that only the participants in the population of no impact by dosing pause are included.

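### The dosing-pause 'no impact' set is defined only at Week 26 but reused at Week 50, where it is the only pause analysis for the binary endpoints

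*SAP*

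**What the plan says.** SAP 4.2.3 defines the no-impact population once: participants with "at least one valid 24-hour urine collection obtained within 3 weeks prior to the Week 26 Visit before dosing pause". Table 4 uses it for the primary endpoint, in the row described as "excluding participants impacted by dosing pause".

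SAP 4.3.2 carries the same set to the key secondary endpoints at Weeks 26 and 50 and gives no Week 50 version:

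- **Proteinuria change to Week 50 (4.3.2.1) and eGFR (4.3.2.3).** Two analyses each. One restricts to the no-impact set. The other runs the usual model "except that dosing pause would be regarded as intercurrent event" (proteinuria), with the same device for eGFR: "dosing pause would be regarded as intercurrent event".
- **>30% and >50% reduction (4.3.2.2).** One analysis: "except that only participants in the population of no impact by dosing pause are included".
- **CRR (4.3.2.4).** One analysis: "only the participants in the population of no impact by dosing pause are included".
- **PRR (4.3.2.5).** One analysis: "as described in Section 4.3.1.5, except that only the participants in the population of no impact by dosing pause are included".
- **Partial remission (4.3.2.6).** One analysis: "as described in Section 4.3.1.13, except that only the participants in the population of no impact by dosing pause are included".

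On missing data, SAP 4.1.4 assumes that outcomes missing because of the pause are missing at random. It lists the pause next to additional standard-of-care therapy and treatment discontinuation, and refers the handling of intercurrent events to the analysis sections. SAP 6.1.8, 6.1.10 and 6.1.11 set CRR, partial remission and PRR to missing when both collections are missing. Table 6 and the nonresponder rules in 4.3.1.2, 4.3.1.4, 4.3.1.5 and 4.3.1.13 name treatment discontinuation but not the pause.

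**The concern.** A sensitivity analysis for the pause should compare the full result with one from participants whose outcome the pause could not have touched. At Week 26 the set is tied to the right visit. At Week 50 it is not: the test is still whether a Week 26 collection came before the pause, and that says nothing about whether the participant was still on schedule up to Week 50, 24 weeks later.

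For the continuous endpoints the damage is limited, because the companion analysis sets data from the pause onward to missing. The Week 50 binary endpoints have no such companion. If their restricted analysis agrees with the main one, a reader may conclude that the pause made no difference, when the restricted set still holds participants assessed after the pause began.

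**Working it through.** The plan states no figure to reproduce here, so the check is calendar arithmetic followed by an illustration.

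**Inputs.** Pause start 06 Sep 2024 (SAP 1), so the last pause-free day is 05 Sep 2024. Week 26 is Day 183 and Week 50 is Day 351 (Protocol 4.4). Day N is first dose + (N − 1) days. The Week 50 collection window opens 3 weeks before the visit for proteinuria change and for >30%/>50% reduction (SAP 4.2.1), and 2 weeks before for CRR, PRR and partial remission (SAP 4.3.1.4, 4.3.1.5, 4.3.1.13). The extra week after the visit that 4.2.1 allows for IgAN at Week 50 does not change when the window opens.

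**Latest entry that can qualify as not impacted.** The Week 26 window opens on Day 183 − 21 = Day 162, which is first dose + 161. This must fall by 05 Sep 2024: 05 Sep 2024 − 161 days = 28 Mar 2024.

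**Earliest entry whose Week 50 window lies wholly after the pause began.**
- 3-week window: opens Day 330 = first dose + 329. 06 Sep 2024 − 329 days = 13 Oct 2023.
- 2-week window: opens Day 337 = first dose + 336. 06 Sep 2024 − 336 days = 06 Oct 2023.

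**Entry dates that are in the set with no pre-pause Week 50 window.**
- 3-week: 13 Oct 2023 to 28 Mar 2024 = 168 dates.
- 2-week: 06 Oct 2023 to 28 Mar 2024 = 175 dates.
- Moving the Week 50 visit by its ±7-day protocol window gives 161 to 175 and 168 to 182.

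**How much of this lies in the documented pause.** SAP version 3.0, dated 12 Nov 2024, still describes dosing as paused; no restart date is given. 12 Nov 2024 − 350 days = 28 Nov 2023. So for first doses from 13 Oct (3-week) or 06 Oct (2-week) to 28 Nov 2023, that is 47 or 54 dates, nominal Week 50 falls while the pause is known to be in force.

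**Cut-off for an unaffected Week 50.** Day 351 = first dose + 350, so scheduled Week 50 precedes the pause if first dose is by 05 Sep 2024 − 350 days = 21 Sep 2023.

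**Illustration of leverage (assumptions, not data).** Take an LN arm with all 30 planned participants in the set. Suppose *k* of them have Week 50 after the pause began and about 40% of the rest respond. The rate without the *k* is compared with the range possible when their observed values are used, from none to all responding.

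| *k* of 30 | Without them | With them as observed |
|---|---|---|
| 3 | 11/27 = 40.7% | 11/30 to 14/30 = 36.7% to 46.7% |
| 6 | 10/24 = 41.7% | 10/30 to 16/30 = 33.3% to 53.3% |
| 12 | 7/18 = 38.9% | 7/30 to 19/30 = 23.3% to 63.3% |

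These are logical bounds for an assumed *k*. The documents give no enrolment by date, so the true *k* is unknown.

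**The case against.** Four objections deserve an answer.

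1. **The SAP does have rules for the pause.** A reader might infer from the silence of the binary sections that nothing covers it. The documents do not support that: 4.1.4 gives a missing-at-random assumption and 6.1.8, 6.1.10 and 6.1.11 say when a response is missing. This stands. What is left uncovered is the Week 50 value that was actually observed during the pause.

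2. **Paused participants are not automatic nonresponders.** A reader might infer that the nonresponder rules catch them. That is the less natural reading. SAP 4.1.4 lists the pause apart from treatment discontinuation, 6.2.1 counts it apart from discontinuations, the version history calls it temporary, and 4.2.3, 4.3.2.1 and 4.3.2.3 make it an intercurrent event only by exception. This also stands, so no percentage-point swing should be built on nonresponder coding. It does not help the restricted set, however: used as observed, these values still enter an analysis meant to be free of the pause.

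3. **The Table 4 label concerns the primary endpoint only.** Correct. Its wording is not a claim about Week 50. But 4.3.2 is headed as sensitivity analysis for the pause and uses the same set for that purpose, so the mismatch is there without the label.

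4. **Little depends on it.** No decision rule uses these results, and secondary analyses are descriptive and unadjusted. This limits the weight of the point but does not remove it: followed exactly, the SAP admits participants to the set who do not belong there.

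**Conclusion.** The point holds in a bounded form. The no-impact set is right for Week 26 and wrong for Week 50. On nominal visit days, 168 entry dates (3-week window) or 175 (2-week window) allow a participant into the set whose entire Week 50 window comes after the pause began. For >30%/>50% reduction, CRR, PRR and partial remission at Week 50, this is the only pause analysis, so it cannot show what the pause did. Beyond the general missing-at-random statement and the missing-collection rules, nothing covers Week 50 values observed during the pause.

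A reader might go further and infer that the trial's main conclusion is at risk. The documents do not support that: the primary test is run on the Full Analysis Set at Week 26 and does not use this set. Nor can the number of participants or the shift in any rate be stated, because enrolment by date and the restart date are not given. The conclusion rests on nominal visit days and on the pause date in the SAP. It is worth correcting before the Week 50 analysis.

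**What to change.** Keep the current set for Week 26 and make three changes for Week 50.

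1. **Week 50 set by entry date.** For every Week 50 analysis in 4.3.2, include participants whose scheduled Day 351 falls before 06 Sep 2024, that is, first dose by 21 Sep 2023. Keep both completers and earlier discontinuers or withdrawals, under the usual intercurrent-event rules. Treat any Week 50 value dated on or after 06 Sep 2024 as missing under the existing rules. Do not define the set by having a pre-pause Week 50 collection. That would keep completers first dosed from 22 Sep to 12 Oct 2023 (3-week, 21 dates) or to 05 Oct 2023 (2-week, 14 dates) and lose earlier discontinuers, who are nonresponders by rule, so response rates would be pushed up.

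2. **Companion analysis for the Week 50 binary endpoints.** Add the analysis already planned for proteinuria change and eGFR, with the pause regarded as an intercurrent event similar to treatment discontinuation. Under the binary rules this scores affected participants as nonresponders, so label it accordingly.

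3. **Main analysis.** State that the pause alone is not treatment discontinuation, and hence that Week 50 values observed during it are used as they stand.

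Cost: a short SAP amendment, one extra flag, one extra table per endpoint, and a smaller Week 50 set.
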